5.3.2.1 Neuro-psychiatric Questionnaire

As part of the overall assessment of subjects and their mental state, and collation of neurological and psychiatric AEs, the CDI [50] will be used in subjects ≥ 7 years of age to evaluate the presence and severity of specific depressive symptoms. It is stressed that use of the CDI should not replace the overall assessment of subject's mental state that should be undertaken before and during treatment, and investigators should consider these assessments in the context of previous medical and psychiatric history. The CDI will be performed at screening and baseline for all subjects and then post-baseline for treated subjects as per the schedules in Table 2 to Table 4. CDI should be performed prior to the completion of other study assessments. *Note: If a subject is <7 years old, but turns 7 years old during the study and within the scheduled CDI administration period, the CDI should be administered from that point onward. For 17-year-old subjects who turn 18 years old during the study, the CDI should continue to be administered.*

Parents or subjects may not be comfortable with certain sentences, or question the sensitive or personal nature of some sentences, and therefore it should be clearly explained that the CDI is just a tool that all subjects in the study are required to complete as part of the assessment of mood disorder problems.

The CDI Item Form will be provided in the subjects' own language, if available. All subjects should complete the form themselves. For younger children or those with reading difficulties or who are unable to read, the instructions and items should be read aloud to the child, then the child will select an answer themselves. If the CDI Item Form is not available in the subject's own language, a translator may read the instructions and items to the child and then the child will select an answer themselves. *The mode of administration (self-administered or translator/caregiver administered) should be clearly*

documented in the clinical records. If subjects feel none of the sentences for an item applies to them, then they should be instructed to choose as best they can. Subjects should be debriefed after the CDI has been completed to address any questions or concerns.

Once the subject has finished the item form, investigational site staff will then complete the CDI Scoring Page and transfer the five subscale scores to the eCRF. Site staff will then add up the five subscale scores to obtain the total CDI score. *Note: If >10% of items (i.e., more than 3 items) are unanswered, the assessment should be considered invalid/incomplete, and the data should not be entered onto the eCRF.*

Follow up of Subjects with Symptoms of Major Depression or Potential CDI Indicators

Whether the CDI is administered or not, investigators should still assess the mental state of their subjects per their standard clinical practice. If any subject exhibits symptoms of major depression and/or if CDI total score is >19 and/or the subject fails to complete all items on the CDI, then the investigator will perform a more thorough evaluation to determine if major depression has developed. If major depression is confirmed by the Investigator, then the subject will be referred to a mental health professional (e.g., counsellor). If this is at screening or baseline, then the subject will be excluded from the study. While in the study, the investigator will determine whether AE criteria have been met and report as an AE on the eCRF, if appropriate (see Section 7.1). If whilst on study the subject is found to have severe depression, PEG-IFN must be permanently discontinued and the subject referred for psychiatric intervention (as per Section 6.2.1 and Section 6.2.5.5).

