4.6.6 Child Depression Inventory (CDI)

Child Depression Inventory (CDI) is a questionnaire that has been validated for children ages 7-17 years old to assess a range of depressive symptoms (Kovacs 1992). In primary CSR, CDI scores from study beginning to 24 weeks after the end of treatment/principal observation period will be reported.

A list of patients, with a CDI raw score >19 (with or without an AE of depression) will be provided for Safety Population.

The total T-scores are standardized scores with a mean of 50 and a standard deviation of 10 derived from a normative samples of 1226 Florida public school students (see CDI manual in [Kovacs 1992] for more details).

The total T-score at each visit, and its change from baseline to week 12, 24, 36, 48 during treatment/principal observation period and at week 4 of initial follow-up, will be summarized for Safety Population.

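### CDI forms with more than 3 blanks trigger a depression evaluation but are kept off the eCRF, so the SAP's CDI output omits one of the protocol's own CDI triggers

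*Protocol*

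**What the plan says.** Protocol 5.3.2.1 (Neuro-psychiatric Questionnaire) does four things that bear on this point.

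- It sets the triggers for a closer look by the investigator. Besides clinical symptoms, there are two from the questionnaire. One is a score threshold: "if CDI total score is >19". The other is non-completion: "and/or the subject fails to complete all items on the CDI, then the investigator will perform a more thorough evaluation". The second applies to any unanswered item.
- It defines an unusable form ("If >10% of items (i.e., more than 3 items) are unanswered") and says what to do with it: "the assessment should be considered invalid/incomplete, and the data should not be entered onto the eCRF".
- It limits what reaches the database. Staff complete a scoring page and "transfer the five subscale scores to the eCRF". No item-level data and no count of blanks are mentioned.
- It forms the total by addition: "Site staff will then add up the five subscale scores to obtain the total CDI score". It gives no rule for forms with 1 to 3 blanks.

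SAP 4.6.6 plans two outputs. One is a listing: "A list of patients, with a CDI raw score >19 (with or without an AE of depression) will be provided for Safety Population". The other is a summary of total T-scores by visit and their change from baseline to Weeks 12, 24, 36 and 48 and follow-up Week 4. There is no missing-item rule and no listing or count of incomplete forms.

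After baseline, the CDI is given only to children treated with PEG-IFN (Protocol 5.3.2 and 5.3.2.1).

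**The concern.** The protocol regards failure to finish the form as a possible sign of depression, then discards the forms on which that failure is most marked. The SAP wants high scorers listed whether or not a depression adverse event was reported, so the listing is meant to show signals that the investigator did not turn into an event. Non-completion is the other questionnaire signal in the protocol, and it has no counterpart in the output.

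At stake is the completeness of a descriptive safety output for a drug where severe depression is a mandatory reason to stop treatment (Protocol 6.2.1) and neuropsychiatric disorders are a named warning (Protocol 7.3). The monitoring board reviews individual and aggregate safety data (SAP 3.2). CDI data that never enter the eCRF may not reach it.

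**Working it through.** **Step 1. Follow each kind of form through the plan.** The trigger and entry columns come from Protocol 5.3.2.1, the listing column from SAP 4.6.6. Totals are as recorded.

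| Blanks | Recorded or partial sum | CDI trigger for evaluation? | On eCRF? | In the SAP listing? |
|---|---|---|---|---|
| 0 | 19 or less | No | Yes | No |
| 0 | above 19 | Yes, score | Yes | Yes |
| 1 to 3 | 19 or less | Yes, incomplete | Yes, blanks not shown | No |
| 1 to 3 | above 19 | Yes, both | Yes, blanks not shown | Yes |
| more than 3 | 19 or less | Yes, incomplete | No | No |
| more than 3 | above 19 | Yes, incomplete at least | No | No |

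Five of the six rows trigger an evaluation and two of those five reach the listing. These are kinds of form, not frequencies. In the last row, if item scores cannot be negative (an assumption; the documents do not give the item range), answering the remaining items could only leave the total above 19. That child would have been listed had the form been finished.

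**Step 2. Can the database tell an invalid form from one never given?** The only CDI fields described are five subscale scores. Both cases leave them empty. They differ in the database only if an adverse event was reported, which is left to the investigator's judgement.

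**Step 3. Check the cut-off.** The protocol equates more than 10% of items with more than 3 items. With J items, the two agree only if 3 blanks do not exceed 10% (3/J ≤ 0.10, so J ≥ 30) and 4 blanks do (4/J > 0.10, so J < 40). They agree for J = 30 to 39. For 20 to 29 items, 3 blanks already exceed 10% (3/20 = 15.0%, 3/29 = 10.3%), yet the form passes the count rule. At J = 40, 4 blanks are exactly 10%, so the count rule rejects a form that the percentage rule accepts. The documents do not state J, so the plan's equivalence cannot be confirmed from them.

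**Step 4. How much could 1 to 3 blanks matter?** This is conditional: it supposes that blanks score zero, which the documents do not say, and that the missing items would have scored at the child's own average. The pro-rated total is S × J/(J − m) for a plain sum S with m blanks. Over an assumed J of 20 to 39, the sums of 19 or less that would newly pass 19 are:

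- 1 blank: 19 only (19 × 39/38 = 19.5; 19 × 20/19 = 20.0).
- 2 blanks: from 18 or 19 upward, depending on J.
- 3 blanks: from 17 or 18 upward (17 × 20/17 = 20.0; 18 × 39/36 = 19.5).

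So even on that supposition the effect at the cut-off is confined to recorded sums of 17 to 19.

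**The case against.** The strongest reply is that the CDI is only a supporting tool. Any blank item, not just more than 3, prompts an evaluation. Mental state is assessed whether or not the CDI is given. Depression events enter the eCRF as adverse events, and SAP 4.6.2 lists all of them. The CDI is repeated, so a child missed at one visit can be listed from another. Post-baseline CDI data involve no Group A versus Group B comparison and no test. All of this stands and keeps the point small. It does not fill the gap, because the listing is meant to include children without a depression event, and for those with an invalid form the plan offers no CDI entry.

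A reader might infer more than the documents support:

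- **That depression is under-counted.** This is not shown. Adverse events have their own route, and blanks may reflect reading difficulty, language or discomfort with sensitive items, all foreseen in Protocol 5.3.2.1. The direction of any bias in the T-scores is unknown for the same reason.
- **That forms with 1 to 3 blanks are summed with blanks as zero.** The protocol says only that subscales are added. The scoring page and instrument manual are not in the documents and may contain a rule.
- **That nothing is kept.** Only eCRF entry is withheld. Sites hold source documents (Protocol 15.1), and the evaluation is still required.
- **That a known share of assessments is affected.** No rate of incomplete forms is given, and children are told to choose an answer as best they can.

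Leaving invalid forms out of mean T-scores is also defensible. Finally, table layouts and data specifications sit in separate modules (SAP Section 1) that are not available here and could already add a flag. Even so, the protocol's instruction not to enter the data would conflict with using it.

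**Conclusion.** The point holds as a minor, easily corrected gap. Protocol 5.3.2.1 treats incompleteness and a total above 19 alike as triggers. The eCRF instruction and SAP 4.6.6 together report only the second, and omit forms whose partial sum already exceeds 19. In the database as described, an invalid form without an adverse event cannot be told apart from a CDI that was not done.

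The consequence is limited to the descriptive CDI output, which after baseline covers PEG-IFN-treated children only. Neither the primary result nor the capture of depression adverse events is affected. The number of forms involved is unknown. The conclusion rests on the eCRF fields being those the protocol describes and on the separate specification modules not adding others.

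**What to change.** 1. In Protocol 5.3.2.1, replace the instruction not to enter invalid forms with entry of every CDI administration, recording the number of unanswered items, the partial sum and a validity flag.
2. Keep invalid forms out of the T-score summaries in SAP 4.6.6, and say so there.
3. In SAP 4.6.6, list incomplete forms beside raw scores above 19, showing the partial sum and any depression adverse event.
4. State in the SAP that forms with 1 to 3 blanks are scored by the instrument manual's rule, citing it. Pro-rating should not be imposed without seeing that rule.
5. While editing the sentence, check that the percentage and the count in the validity cut-off agree for the form's actual number of items.

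The cost is a few extra eCRF fields and a slightly longer listing. No visit, test or clinical rule changes.

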5.4 LABORATORY ASSESSMENTS

Laboratory assessments post-screening are noted in [Table 6](#) and will be carried out as per the schedules in [Table 2](#) to [Table 4](#).

Table 6 Laboratory Assessments

Hematology ^a	Complete blood count (hemoglobin, hematocrit, total WBC count, differential WBC count [neutrophils, lymphocytes, monocytes, eosinophils, basophils]), platelet count], INR
Clinical chemistry ^a	ALT, AST, GGT, total bilirubin, alkaline phosphatase, total protein, albumin, BUN/urea, creatinine ^d , uric acid, total calcium, phosphorus, cholesterol, triglycerides, random glucose, sodium, chloride, potassium
Urinalysis ^b	Dipstick with subsequent microscopic evaluation if positive for blood.
HCG pregnancy test ^b	Urine or serum pregnancy test for females of childbearing potential at any time secondary amenorrhea of more than 1 week occurs. The result of the baseline pregnancy test must be available prior to randomization and commencement of treatment.
Thyroid function tests ^c	FT3, FT4, TSH, TPO antibodies ^e
Immunology ^c	ANA ^e
HBV serology and virology ^c	HBeAg, anti-HBe, HBsAg, anti-HBs, quantitative HBsAg and HBeAg, HBV-DNA

^a To be performed by a local laboratory in countries activated prior to April 2013, and by a central laboratory in countries activated after April 2013.

^b To be performed by local laboratory.

^c To be performed by central laboratory.

^d Estimated creatinine clearance will be calculated by the Sponsor at Week 24/SW 24.

^e PEG-IFN–treated subjects only.

Samples for central analysis will be sent to one or more central laboratories or to the Sponsor for analysis.

Where any analysis is performed by a local laboratory, normal ranges for the local laboratory parameters must be supplied to Roche or designee before the study starts and at any point that the normal ranges are changed.

The results from all hematology and clinical chemistry investigations should be available and reviewed by the investigator or his/her authorized designee before instructing the subject on whether PEG-IFN dosing should continue unchanged or be modified.

See Section 6.2.5 and 7.1.3.1 for follow-up of laboratory abnormalities.

All virological and serological efficacy parameters will be assessed by the central laboratory.

The total volume of blood loss for laboratory assessments (excluding PK and RCR) will be approximately as follows:

- Group A and Group C: 228 mL
- Group B non-switch: 158 mL
- Group B switch: up to 312 mL

The procedures for the collection, handling, and shipping of laboratory samples are specified in the Sample Handling and Logistics Manual for this study. All remaining blood samples will be destroyed no later than 18 months after the final closure of the study database.

The samples for this study should be classified, packed, and shipped as UN3373 Biological Substance, Category B.

5.4.1 Serum Bank and Exploratory HBV Markers

Additional serum bank samples (included in the blood volumes in Section 5.4) will be collected during the course of this study (as per the schedules in Table 2 to Table 4). The primary purpose of these samples is to repeat laboratory tests outlined in the Schedule of Assessments should there be a problem with the original sample. In the event that repeat testing is required, sites will be informed whether the sample should be transferred to the central laboratory for retesting (e.g., HBV serology) or whether it is a test that should be repeated locally (e.g., ALT).

The secondary intention is to use residual serum bank samples for exploratory HBV biomarker analyses. This secondary use of serum bank samples is optional and only applies to subjects who have consented to RCR sample collection and analyses (see Section 5.4.3). After confirmation that serum bank samples are no longer required for repeat testing, any remaining serum bank samples, either at investigational sites or at the central laboratory, may be used for DNA and/or non-DNA biomarker analyses. Samples still at the site may remain stored at the site or can be transferred to the central laboratory for storage until required for biomarker analyses. Example biomarker analyses include viral factors and sequencing and host response factors to infection and treatment. Protection of subject confidentiality will extend to any data generated from the assaying of these samples (see Section 17).

All remaining serum bank samples, either at the site or central laboratory, will be destroyed no later than 18 months after the final closure of the study database.

5.4.2 Pharmacokinetic Assessments

For sites taking part in the PK sub-study, consenting/assenting subjects assigned, randomized or switching to PEG-IFN will have blood samples (approximately 1 mL) collected to evaluate the PK of PEG-IFN during Weeks 1 and 24 pre-dose (0), and 24–48, 72–96, and 168 hours after administration of PEG-IFN. (See also footnote to

[Table 7.](#)) Blood samples designated as pre-dose must be collected within 6 hours prior to PEG-IFN administration.

For scheduling purposes, time windows are provided for the first two post-dose samples during Weeks 1 and 24. The first post-dose blood sample should be collected within 24 to 48 hours after the dose. The second post-dose blood sample should be collected between 72 and 96 hours after the dose. There must be at least 48 hours between the two blood samples. The 168-hour blood sample will be collected within 6 hours before the next dose is administered.

Pre-dose samples will also be collected at Weeks 4, 8, and 12 within 6 hours prior to PEG-IFN administration ([Table 7](#)). Subjects should take all doses of PEG-IFN associated with both pre- and post-dose PK sampling at the clinic.

The procedure for the collection and handling of blood samples for PK analysis is specified in the Sample Handling and Logistics Manual. The exact date and time of dosing and collection of blood samples will be recorded in the source document and eCRF. The serum concentrations of PEG-IFN will be assessed by a quantitative enzyme-linked immunosorbent assay (ELISA). PK parameters, such as the maximum concentration (C_{max}), area under the curve (AUC), clearance (CL/F) and volume of distribution (V/F), if possible, will be estimated using either non-compartmental analysis or a population approach.

The target exposure is based on the mean exposure observed in adults treated at 180 μg in clinical studies (3334 to 4348 $\text{ng} \cdot \text{h/mL}$) and the mean exposure observed in children in Study NR16141 treated at a dose of 180 $\mu\text{g}/1.73 \text{ m}^2 \times \text{BSA}$ (5667 $\text{ng} \cdot \text{h/mL}$). When adequate PK data have been collected over the first 24 weeks for at least 15 PEG-IFN-treated subjects, ideally with representation from all BSA categories, PK analysis will be undertaken to ensure exposure is in the appropriate therapeutic range. If data suggest that the exposure is not in the appropriate range, an adjustment to the dosing regimen will be made to meet the target exposure range.

Once PK data up to Week 24/switch Week 24 are available for at least 5 to 10 subjects in each BSA category, PK sampling will be stopped. However, the sub-study may be ceased even if data from a minimum of 5 subjects in each BSA category are not obtained in the case of excessively long recruitment times.

The relationship between PK and PD parameters may also be explored.

Any PK sample residues may be used for analysis of exploratory HBV markers (see Section [5.4.1](#)).

The total volume blood loss for PK assessments will be approximately 14 mL.

Table 7 PK Sampling Schedule

	Baseline/ Switch Baseline	Week 4/ Switch Week 4	Week 8/ Switch Week 8	Week 12/ Switch Week 12	Week 24/ Switch Week 24
0 hour (pre-dose)	x				x
Pre-dose		x	x	x	
24–48 hours post-dose	x				x
72–96 hours post-dose ^a	x				x
168 hours post-dose	x ^b				x

^a At least 48 hours after the previous blood sample.

^b Equates to Week 1 visit.

5.4.3 Roche Clinical Repository Specimen(s)

For sites opting to take part, specimens for the RCR will be collected from subjects who give specific consent/assent to participate in this optional research. The results of specimen analysis from the RCR will facilitate the rational design of new pharmaceutical agents and the development of diagnostic tests, which may allow for individualized drug therapy for subjects.

RCR samples will be collected as per the schedule in [Table 2](#) to [Table 4](#). For all RCR samples, dates of consent/assent and specimen collection should be recorded on the associated RCR page of the eCRF. For sampling procedures, storage conditions, and shipment instructions, see the Sample Handling and Logistics Manual.

RCR specimens will be destroyed no later than 15 years after the date of final closure of the associated clinical database. The RCR storage period will be in accordance with the IRB/IEC-approved Informed Consent Form and applicable laws (e.g., health authority requirements).

Specimens for dynamic (non-inherited) biomarker discovery and validation will be used for research purposes to help to better understand the pathogenesis, course, and outcome of CHB and related diseases, and identify dynamic biomarkers that are predictive of response to PEG-IFN treatment (in terms of dose, safety, and tolerability). Specimens for dynamic biomarker discovery will be subject to the confidentiality standards described in [Section 17](#). The following samples will be collected for identification of dynamic (non-inherited) biomarkers:

- Whole blood for isolation of plasma
- Whole blood for RNA expression analysis

Specimens for genetic (inherited) biomarker discovery and validation will be used for research purposes to hopefully help improve subject outcome by predicting which subjects are more likely to respond to specific drug therapies, predicting which subjects are susceptible to developing adverse side effects and/or predicting which subjects are

likely to progress to more severe disease states. Such genetic biomarker specimens will undergo additional processes to ensure confidentiality, as described in Section 17. The following samples will be collected for identification of genetic (inherited) biomarkers:

- One time whole blood sample for DNA isolation

Total blood volume collected for RCR sampling will be approximately as follows:

- Group A and Group C: 36 mL
- Group B non-switch: 36 mL
- Group B switch: up to 54 mL

5.5 SUBJECT MEDICATION DIARY REVIEW

Subjects treated with PEG-IFN will complete a Subject Medication Diary (SMD), which the family will bring to each study visit. The information will be reviewed with the family by the Clinic Coordinator at each study visit. It is mandatory that each PEG-IFN injection dose be recorded in the SMD. The parent/guardian will be instructed to record the date and dose of PEG-IFN. The person giving the PEG-IFN injection must initial the SMD. During the diary review, the reviewer will correct unreadable information and ask the subject to supply missing information. Reviewers will report missing doses, dose adjustments, and treatments stops or restarts on the eCRF. Subject diaries will be maintained with the source documents at each site. See also Section 6.5.2.

